### 5.2.4. Lectin and Antibody Labeling of Muscle Biopsies

Frozen slides acquired from subjects' muscle biopsies will be stained with fluorescent-labeled lectins and imaged by (quantitative) confocal microscopy. As mentioned, we and others have demonstrated by lectin staining that in particular O-linked glycans in GNE myopathy subjects and in a GNE myopathy mouse model are hyposialylated. Sialylation of muscle glycans recovered to normal levels in our GNE myopathy mouse model after ManNAc therapy. This method is the only reported reproducible, quantifiable assessment of muscle glycan hyposialylation in GNE myopathy to date (Figure 8).

### 5.2.5. Potential Biomarkers

#### 5.2.5.1. Intracellular Biomarkers

We will use white blood cell pellets to explore the intracellular concentrations of ManNAc, Neu5Ac and CMP-Neu5Ac after administration of ManNAc. CMP-Neu5Ac, the end product of the sialic acid biosynthesis pathway and the donor of sialic acid to nascent glycoproteins and glycolipids in the Golgi apparatus, may be a useful marker of improved intracellular sialic acid biosynthesis (Figure 1). An LC-MS/MS method is being developed to quantify ManNAc, Neu5Ac and CMP-Neu5Ac in human WBCs. Samples from this study will be stored and tested when the method is validated.

[figure not shown]
### 5.2.5.2. Blood Biomarkers

Plasma sialylated proteins are being explored as potential biomarkers, in particular those with mucin-like O-glycan structures. We have data that show the ratio of the plasma O-glycan structures Thomson-Friedenreich (T)-antigen versus Sialyl T-antigen (T/ST ratio) is abnormal in subjects with GNE myopathy. We have anecdotal evidence that the plasma T/ST ratios normalized in GNE myopathy subjects that received sialylation-increasing therapies (including IVIG, off-label ManNAc, sialic acid). Exploratory glycan analysis will be performed on subjects' blood to identify biomarkers and assess their response to ManNAc therapy.

### 5.2.5.3. Urine Biomarkers

Exploratory glycan analysis will be performed on subjects' urine to identify (sialylated) biomarkers and assess their response to ManNAc therapy.

**Figure 8. Muscle Lectin Histochemistry**

A. Human muscle sections from biceps (Control and Patient 1) and gastrocnemius (Patient 2) were stained with three lectins (green) informative for sialylation status and co-stained with the nuclear dye DAPI (blue). GNE myopathy muscle specimens show selective hyposialylation compared to control muscle, demonstrated by apparent normal staining of WGA (*Wheat Germ Agglutinin*, binding to most sialic acid groups, independent of linkage), but decreased staining of SNA (*Sambucus Nigra Agglutinin*, predominantly binding sialic acids in a  $\alpha(2,6)$ -linkage to their underlying monosaccharide; this linkage is abundant on O-linked glycans). In addition, staining of VVA (*Vicia Villosa Agglutinin*, predominantly binding terminal GalNAc, without sialic acid attached, O-linked to serine or threonine residues of glycoproteins) was increased in GNE myopathy muscle specimen compared to control, indicating hyposialylation of O-linked glycans (see also refs).

B. Mouse muscle sections (gastrocnemius) from ~ 6 months old GNE myopathy mice (-/-, unfed) showed similar hyposialylation of O-linked glycans as human GNE myopathy subjects (see A) when compared to an age-matched control (Control unfed). Oral supplementation of ManNAc (1 g/kg/day) for 12 weeks restored the muscle sialylation status back to the normal range (-/- + ManNAc), demonstrated by increased SNA and decreased VVA signal intensities similar to control specimens (see ref).

All images are 1D projections of confocal Z-stacks. All imaging was performed at the same microscope intensity settings per lectin per species (with a 63  $\times$  objective).

### 5.3. Biological Specimens

#### 5.3.1. Samples for Safety, Pharmacokinetic, and Pharmacodynamic Evaluations

Blood and urine will be collected for safety, PK and PD evaluations (see [Appendix D](#) for timepoints). The blood draw for safety labs at Day 450, 638 and 912 ( $\pm 30$ ) will be performed at the NIH clinical center, or the subject's home physician office or local laboratory. Samples will be stored without personally identifiable information (PII) per the lab manual. Collection, handling, and shipping procedures for plasma samples for PK are provided in the Laboratory Manual.

#### 5.3.2. Research Samples

At the discretion of the investigator, blood and urine (first morning void) may be collected for future research. The amount of blood that may be drawn for research purposes shall not exceed 10.5 mL/kg or 550 mL, whichever is smaller, over any eight-week period. This is in compliance with the NIH Clinical Center guidelines.

Blood, urine, and derivatives thereof (e.g., RNA/DNA, platelets, red blood cells, white blood cells, urine exosomes) collected under this protocol will be stored for future research not specifically outlined in this protocol. Such research could involve, but is not limited to, molecular, proteomic, biochemical, glycomic, and metabolomic analyses of these samples. Future research using these samples will relate to GNE myopathy.

For subjects also enrolled in the ongoing Natural History study (11-HG-0218), sample volume safety limits will take into account both protocols.

**Table 7. Blood Volume**

Sample (Day)	Hematology 	ESR	PT/PTT	Chemistry 	PK	PD	Future Research	Total daily volume
Volume	3	3	4.5	4	3	20	10-50	--
D0	3	3	4.5	4		20	50	84.5
D1					30	80		110
D2					3			3
D3	3	3	4.5	4	3	20	20	57.5
D5					3			3
D7	3	3	4.5	4	30	20	30	94.5
D9	3	3	4.5	4		20	20	54.5
D45	3	3	4.5	4	3	20	50	87.5
D85	3	3	4.5	4	3	20	40	77.5
D90					30	20		50
D91					3			3
D92	3	3	4.5	4	3	20	40	77.5
D93					3			3
D180	3	3	4.5	4	3	20	40	77.5
D365	3	3	4.5	4	3	20	40	77.5

D450	3	3	4.5	4				14.5
548	3	3	4.5	4	3	20	40	77.5
638	3	3	4.5	4				14.5
730	3	3	4.5	4	3	20	40	77.5
820	3	3	4.5	4				14.5
912	3	3	4.5	4	3	-	-	17.5

### 5.3.3. Collaborating Laboratories

After establishing appropriate material transfer agreements and/or contracts, biospecimens collected under this protocol may be sent to the following investigators:

**Table 8. Collaborations**

Sample	Laboratory	Location
PK and intracellular PD	Alliance Pharma	Malvern, PA 19355
Hematology, ESR, PT/PTT and Chemistry	Quest Diagnostics	Multiple locations

Additional laboratories can be added by amendment of this protocol, if they require a material transfer agreement.

### 5.4. Approved Drugs

No approved drugs will be used as part of this study.

### 5.5. Unapproved Drugs

ManNAc drug substance grade ManNAc and other forms of ManNAc are not approved for any indication. The Investigational New Drug (IND) application number for this product is IND #78091.

#### 5.5.1. Identity of Investigational Product

ManNAc (N-acetyl-D-mannosamine monohydrate; trade name ManNAc) will be supplied as a powder by New Zealand Pharmaceuticals. The study drug will be prepared by the NIH Clinical Center Pharmacy as powder-in-bottle. The pharmacy will add 200 mL of water, shake to dissolve the drug, and re-label the bottles appropriately for delivery to the subjects. See [Appendix E](#).

#### 5.5.2. Packaging, Labeling, and Storage of Clinical Supplies

ManNAc will be supplied as a powder, packaged in 8 oz. amber plastic prescription bottles (Berry Plastics Part # PB-8) with a removable label and labeled as an investigational product.

Storage conditions for the study drug will be 2 to 8 °C. For additional details, refer to [Appendix E](#).

### **5.5.3. Drug Accountability**

The study drug will be registered and tracked with the NIH Pharmaceutical Development Service (PDS). Drug supply will be managed by the NIH CC Pharmacy Department. The NIH pharmacy is responsible for the accountability of the investigational product. This will include documentation of receipt, storage, and dispensing of the investigational agent. The NIH pharmacy will return or destroy (per instruction of the IND sponsor) unused investigational drug at the conclusion of the study.

An order for study drug administration will be entered into CRIS by the study staff. The NIH Pharmacy will prepare and send the study drug to the unit. After administration of the study drug, the CC nursing staff will log the administration into CRIS. The empty container will be discarded.

## **5.6. Results Given to Participants**

Subjects enrolled in this study will be told of their medically relevant laboratory results and the results of consultations. They will eventually be informed of the overall results of the study.

## **5.7. Questionnaires**

A diary will be provided to subjects so that symptoms can be recorded after the administration of study drug ([Appendix K](#)). Patient reported outcomes mentioned in [Section 5.2.1.6](#) will be administered as questionnaires.

## **5.8. Genetic Counseling**

In cases where subjects have not received genetic counseling in the past, the Investigator or one of the genetic counselors in the Office of the Clinical Director will perform this service.

## **5.9. Criteria for Withdrawal**

Subjects will be informed that they have the right to withdraw from the study at any time for any reason without prejudice to their medical care.

Subjects may be withdrawn from the study for any of the following reasons:

- Subject request
- Subject is unwilling or unable to comply with the protocol
- Medical reason, at the discretion of the Investigator

In addition, the Sponsor may terminate this study at any time for safety or administrative reasons. The Sponsor will terminate the study if the occurrence of AEs or other findings suggests an unacceptable risk to the health of the subjects.

Subjects who withdraw from the study early should undergo all safety evaluations prior to discharge from the unit. Subjects who withdraw will be replaced. The reason for subject withdrawal must be recorded in the subject's CRF. The Investigator must notify the Sponsor immediately when a subject has been discontinued/withdrawn due to an AE. Subjects who withdraw from the study may request that samples be destroyed.

## 6. DESCRIPTION OF STUDY POPULATION

### 6.1. Estimated Number of Participants

This study will enroll 12 subjects with GNE myopathy divided into two dosing cohorts (cohort size = 6) assigned to receive ManNAc at either 3,000 mg BID or 6,000 mg BID for a 7-day pharmacokinetics study, for a total of 6,000 mg or 12,000 mg per day, respectively. All patients receive 6,000 mg BID for the remainder of the study beyond 7 days. Accrual ceiling will be set at 30 subjects to allow for subject replacement if needed. We anticipate enrollment of the 12 subjects within 1 year.

### 6.2. Eligibility Criteria

#### 6.2.1. Inclusion Criteria

1. Subject is age 18-60 years, inclusive, and of either gender.
2. Subject has a diagnosis of GNE myopathy based upon a consistent clinical course and identification of two *GNE* gene mutations.
3. Subject must be willing to stop any treatment with ManNAc, sialic acid, intravenous immunoglobulin (IVIG), and/or other supplements containing sialic acid (e.g. St. John's wort, sialyllactose) 90 days prior to dosing and remain off such treatment for the duration of the trial.
4. Subjects must have a body mass index (BMI) between 18 and 30 kg/m^2 with a bodyweight of >50 kg
5. Subjects must meet one of the criteria below on at least one of the following muscle groups: 1) ankle dorsiflexion, 2) knee flexion, 3) hip extension, 4) grip, 5) elbow flexion, 6) shoulder abduction:
  - a. 20-75% of predicted strength measured by QMA at baseline, or
  - b. If predicted muscle strength above 75%, a documented change of at least 10% per year.
6. Subject has the ability to travel to the NIH Clinical Center for admissions.
7. Subject has an INR  $\leq$ 1.5 and must have stopped warfarin and other anticoagulants 2 weeks prior and after muscle biopsy procedures. Aspirin and clopidogrel should be stopped 3 days and 5 days before the procedure, respectively.
8. Subject must be able to comply with requirements of the protocol, including blood collection, drug administration, muscle MRI/MRS, muscle biopsy and muscle strength assessments.
9. If a woman of reproductive age, subject must be willing to use an effective method of contraception for the duration of the trial.
10. Subject must be able to provide informed consent.

#### 6.2.2. Exclusion Criteria

1. Subject had a clinical significant infection or medical illness 30 days prior to the first protocol visit.
2. Subject has a psychiatric illness or neurological disease that would interfere with the ability to comply with the requirements of this protocol. This includes, but is not limited to,

uncontrolled/untreated psychotic depression, bipolar disorder, schizophrenia, substance abuse or dependence, antisocial personality disorder, panic disorder, or behavioral problems, which interfere with effective communication.

3. Subject has hepatic laboratory parameters (AST, ALT, GGTP) or renal laboratory parameters (creatinine, BUN) greater than 3 times the upper limit of normal.
4. Subject has known adverse reactions to anesthetic or sedatives utilized for muscle biopsy.
5. Subject is anemic (defined as Hematocrit <30%) or has platelets <100,000 or white blood cell count less than 3,000.
6. Subject shows evidence of clinically significant cardiovascular, pulmonary, hepatic, renal, hematological, metabolic, or gastrointestinal disease, or has a condition that requires immediate surgical intervention.
7. Subject is pregnant or breastfeeding at any time during the study.
8. Subject has received treatment with another investigational drug, investigational device, or approved therapy for investigational use less than 90 days prior to the first protocol visit.
9. Subject has hypersensitivity to ManNAc or in the judgment of the investigator, has a condition that places the subject at increased risk for adverse effects.
10. The presence of persistent diarrhea or malabsorption that could interfere with the subject's ability to absorb drugs or to tolerate ManNAc therapy.

### **6.2.3. Justification of Inclusion/Exclusion Criteria**

The rationale for the study population is that individuals with GNE myopathy will likely process sialic acid differently from healthy normal volunteers due to the hyposialylation characteristic in GNE myopathy, and therefore the PK of ManNAc in healthy normal volunteers may not be predictive of PK in GNE myopathy subjects.

Subjects must be willing to stop treatment with ManNAc, sialic acid, IVIG, and/or other supplements containing sialic acid (e.g. St. John's wort, sialyllactose) 90 days before dosing and remain off these medications for the duration of the trial.

Children are excluded because GNE myopathy generally does not typically manifest in childhood and juvenile toxicology studies have not been performed. Subjects with certain psychiatric illnesses will be excluded because their symptoms could interfere with compliance or communication with health care personnel and therefore the integrity of the trial.

Subjects with coagulation defects or taking anticoagulants are at higher risk of bleeding with muscle biopsy. Only those subjects that can safely stop taking such medications, as determined by their treating physician, will be eligible for this trial.

### **6.3. Location of Study**

NIH Clinical Center.

## 6.4. Recruitment Strategies

Subjects will be recruited from patient organizations such as the Neuromuscular Disease Foundation (NDF) and Advancement of Research for Myopathies (ARM); from groups of subjects known to the Investigators, from individuals previously enrolled in the following studies:

- Protocol 11-HG-0218: “A Natural History Study of Patients with GNE Myopathy”
- Protocol 12-HG-0207: “A Phase 1 Randomized, Placebo-Controlled, Double-Blind, Escalating Single-Dose Study to Evaluate the Safety, Tolerability, and Pharmacokinetics of ManNAc in Subjects with GNE Myopathy or Hereditary Inclusion Body Myopathy (HIBM)”

The study will include females in this early stage of drug development as encouraged by regulatory agencies. Pregnancy tests will be performed before dosing (see 5.2.2.2 and Appendix B).

We will attempt to recruit all minority subjects we are aware of, including individuals from the Iranian Jewish community. A recruitment letter will be mailed to several large minority medical centers to aid with the ascertainment of under-represented subjects. These are listed with a sample of the recruitment letter in Appendix J. These will include:

1. Meharry Medical College  
[name]  
[contact]
2. Morehouse School of Medicine  
[name]  
[contact]
3. Howard University  
[name]  
[contact]
4. Charles R. Drew University of Medicine and Science  
[name]  
[contact]

## 6.5. Existing Sample/Data Sets

Not applicable.

## 6.6. Financial Compensation

None.

## 7. STATISTICAL CONSIDERATIONS

### 7.1. Statistical Plan

An independent statistical analysis will be performed after the study is completed, queries are resolved and the database has been locked.

#### 7.1.1. General Reporting Conventions

Standard descriptive statistics will include the number (n), mean and standard deviation (SD), median, minimum, and maximum values for continuous variables. For categorical variables, the frequency of subjects will be provided along with the percentage based on the number of subjects with available data. Unless otherwise indicated, summaries will be based on observed data (i.e., no missing data will be imputed).

Any statistical testing and/or provided confidence intervals (CI) are provided as an aid in interpreting study results and are not intended as claims. Results from this study may be used in designing future studies.

Summaries will be provided by treatment group for the individual ManNAc treatment groups (6,000 mg and 12,000 mg), a combined ManNAc group and the combined control subjects from all two cohorts.

Analyses will be generated using SAS® version 9.2 or higher. Analysis on QMA will be performed using R®.

### 7.2. Statistical Methods and Evaluations

#### 7.2.1. Demographic and Baseline Characteristics

Baseline and demographic characteristics including age, gender, race, ethnicity, height, weight, BMI, and genotype information will be summarized descriptively by treatment group. The medical history summary will include the number and percent of subjects with one or more findings by body system and treatment group.

#### 7.2.2. Safety Evaluations

All safety data will be listed. AEs, SAEs, unanticipated problems, AEs related to the drug (possible, probable, or definite) and CTCAE Grade 3 and 4 AEs will be summarized overall. These summaries will include the number of events and the number and percentage of subjects with a given event. AEs will also be summarized by system organ class (SOC) and treatment group to identify AEs that occur at a higher frequency in subjects treated with ManNAc at different dose levels.

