## 4. STUDY DESIGN

### 4.1. Study Overview

This is a Phase 2, open-label, single-center study of ManNAc in subjects with GNE myopathy. The study will characterize the safety, tolerability and PK of multiple doses of ManNAc (Pharmacokinetic Phase), intermediate (90-day), and long-term (912 days; 30 months) safety and efficacy of ManNAc (Safety and Efficacy Phase). Twelve subjects will be enrolled into the trial.

Before dosing, subjects will undergo baseline evaluations that include clinical laboratory tests, muscle biopsy, Quantitative Muscle Assessment (QMA), muscle MRI, muscle biopsy and patient-reported outcomes (PROs).

In the pharmacokinetic (PK) phase, subjects will receive one of two doses: 3,000 mg (Cohort A) or 6,000 mg (Cohort B) ManNAc twice daily (BID) for total daily doses of 6,000 and 12,000 mg, respectively for 7 days while admitted to the NIH Clinical Center to assess for PK and safety. Safety and tolerability will be assessed on an individual basis.

In the Safety and Efficacy Phase, if ManNAc was safe and well-tolerated in the PK phase, subjects on Cohort A will be escalated to 6,000 mg BID on Day 7, and safety of the new dose-level will be assessed until discharge on Day 10. Subjects on Cohort B will be maintained at 6,000 mg BID, and if well tolerated they may be discharged on Day 7. After discharge, subjects will self-administer ManNAc at a dose of 6,000 BID for a total dosing duration of 912 days (30 months).

Follow-up visits to the NIH Clinical Center will occur on Day 45 ( $\pm 7$ ), Day 85 ( $\pm 7$ ), Day 180 ( $\pm 14$ ), Day 365 ( $\pm 14$ ), Day 548 ( $-30$ ), Day 730 ( $-30$  days) and Day 912 ( $-30$  days). PK, PD and safety will be evaluated at all visits. Muscle biopsy will be performed only at the baseline and Day 85 visits.

Follow-up phone calls for safety will occur at approximately Days 28, 63, 120, 240, 300, 400, 638, and 820 ( $\pm 30$  days). After Day 912 all Grade  $\geq 2$  AEs at least possibly related to study drug will be followed to resolution.

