#### **4.8. Dose Escalation**

Subjects in Cohort A will receive 3,000 mg of ManNAc BID for 7 days before they are escalated on Day 7 to receive 6,000 mg BID for the rest of the trial. The evaluation of a dose escalation/de-escalation for an individual will initially be reviewed by the Principal Investigator, according to the criteria in Table 5 and reviewed by the Safety Review Committee (SRC) when the Cohort is completed or safety issues arise. The safety information to be reviewed will include AEs, physical exams, vital signs, and clinical laboratory data.

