##### **4.8.2. Initiation and Continuation Rules for Cohort B**

The SRC will review all available safety data for Cohort A of subjects prior to making a decision to initiate Cohort B. The SRC will convene when at least 14 days of safety have been collected on the last subject dosed in Cohort A.

- a. Cohort B will be initiated at 6,000 mg BID provided that there are  $< 2$  subjects in Cohort A that experienced  $\geq 2$  Grade 2 drug-related AEs or  $\geq 1$  drug-related SAE.
- b. If subjects experience  $\geq 2$  Grade 2 drug-related AEs or  $\geq 1$  drug-related SAE, the SRC will be convened to make decisions based on Table 6.

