### **7.4. Interim Analysis**

Interim analyses are planned after each cohort has completed the pharmacokinetic phase, and after each cohort has undergone evaluation at days 182, 365, 548, 730 and 912 (6, 12, 18, 24, and 30 months).

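### A whole-study adverse-event table by treatment group (Section 7.2.2) cannot show a dose effect, because the cohorts are planned at different doses for only about 7 of 912 days

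*Combined protocol and SAP*

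**What the plan says.** Section 7.2.2 first provides overall AE summaries: "These summaries will include the number of events and the number and percentage of subjects with a given event". It then adds a table by system organ class "and treatment group to identify AEs that occur at a higher frequency in subjects treated with ManNAc at different dose levels". That last phrase gives the by-group table its purpose.

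Section 7.1.1 sets the general convention. Summaries are given for the "individual ManNAc treatment groups (6,000 mg and 12,000 mg), a combined ManNAc group and the combined control subjects from all two cohorts", and percentages are based on subjects with available data. Section 7.2.1 uses the same treatment groups for baseline characteristics, and Section 7.3 describes enrolment into two cohorts of six.

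On dosing, Section 4.1 says that in the PK phase "subjects will receive one of two doses: 3,000 mg (Cohort A) or 6,000 mg (Cohort B) ManNAc twice daily". Section 4.8 has Cohort A "escalated on Day 7 to receive 6,000 mg BID for the rest of the trial". Section 6.1 confirms: "All patients receive 6,000 mg BID for the remainder of the study beyond 7 days". The synopsis in Appendix A gives 912 days of dosing and no reference therapy.

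Neither Section 7.1.1 nor Section 7.2.2 states how Cohort A's AEs are assigned after its dose change, what period the by-group table covers, or that exposure time enters it. The Table 6 footnote that pools both cohorts at 6,000 mg BID applies to Safety Review Committee decisions, not to this table.

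**The concern.** The table is meant to reveal AEs that depend on dose, but its columns barely differ in dose once follow-up extends past the first week. On the enrolled-cohort reading, a real dose effect would be diluted, and similar columns could be taken as evidence that dose does not matter. On the dose-at-onset reading without person-time, the lower dose would look safer merely because it was taken for a few days.

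Safety and tolerability is the first primary objective. This is the only AE display by dose that the statistical section describes, and Section 7.1.1 says that results may be used in designing future studies.

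**Working it through.** The plan states no figure to reproduce for this table; the check is exposure arithmetic on planned dosing.

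**Inputs.** Two cohorts of 6 (Section 7.3); about 7 days at 6,000 mg/day for Cohort A (Section 4.8); 12,000 mg/day otherwise (Section 6.1); 912 days in total (Appendix A). The three-times-daily dosing at the last visit keeps 12,000 mg/day and changes nothing here.

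**Planned exposure.**
- Share of Cohort A's time at 12,000 mg/day: (912 − 7)/912 = 905/912 = 99.2%.
- Mean planned daily dose in Cohort A: (7 × 6,000 + 905 × 12,000)/912 = 11,954 mg, against 12,000 mg in Cohort B.
- Person-days at 6,000 mg/day: 6 × 7 = 42. At 12,000 mg/day: 12 × 912 − 42 = 10,902. Ratio 1:260.
- If escalation is counted from the start of Day 7: 6 × 6 = 36 against 10,908, ratio 1:303.

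**Reading 1: group = enrolled cohort, whole study.** Let k be the true rate ratio of 12,000 to 6,000 mg/day. At a constant AE rate the table shows, for Cohort B over Cohort A, k × 912/(7 + k × 905):
- k = 2: 1,824/1,817 = 1.004
- k = 3: 2,736/2,722 = 1.005
- k = 5: 4,560/4,532 = 1.006

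If AEs cluster early, let f be the share of Cohort B's AEs that fall in Days 1-7. Cohort A's expected count relative to Cohort B's is 1 − f(1 − 1/k). For k = 2 the apparent ratio is 1/(1 − f/2):
- f = 10%: 1/0.95 = 1.05
- f = 25%: 1/0.875 = 1.14
- f = 50%: 1/0.75 = 1.33

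Even with half of all AEs in week 1, a doubling appears as 1.33. The values of k and f are assumptions; the documents give neither.

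**Reading 2: group = dose at onset, no person-time.** Assume no dose effect and a constant rate. The chance that a subject has at least one AE is 1 − exp(−rate × time):

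| Assumed AEs per person-year | 7 days at 6,000 mg/day | about 905 days at 12,000 mg/day |
|---|---|---|
| 0.2 | 0.4% | 39% |
| 0.5 | 1.0% | 71% |
| 1.0 | 1.9% | 92% |

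Expected event counts would stand in the ratio of person-days, 260 to 1. With early clustering the count ratio is (12 − 6f)/(6f): 19, 7 and 3 for f = 10%, 25% and 50%. Each is an apparent excess at 12,000 mg/day where none exists.

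**After the repair.** In Days 1-7 each cohort has 6 × 7 = 42 planned person-days, so a true ratio of 2 is expected to appear as 2. The precision is poor: Fisher's two-sided p is 0.061 for 0/6 against 4/6 and 0.015 for 0/6 against 5/6. For 0/6 the exact 95% upper limit is 1 − 0.025^(1/6) = 46%.

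**The case against.** The strongest reply is that the plan is not silent. Section 7.1.1 names the groups and ties them to the cohorts, Section 7.2.1 uses them for baseline data, where dose at onset has no meaning, and Section 7.1.1 gives a subject denominator. This stands. A reader might infer that group and denominator are wholly undefined, but the documents do not support that. What is missing is the assignment rule after Day 7, the window and the person-time. The enrolled-cohort reading does not save the table, since it is the one that dilutes.

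A reader might also take 260-fold as the size of the problem. That is an event-count ratio on the less supported reading, at a constant rate; a table of subject percentages would not show it.

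Section 7.4 says "Interim analyses are planned after each cohort has completed the pharmacokinetic phase". It is tempting to infer that this interim is already contaminated. Section 4.8.2 delays Cohort B: "The SRC will convene when at least 14 days of safety have been collected on the last subject dosed in Cohort A". By the time Cohort B completes its 7 days, each Cohort A subject would have at least 14 + 7 = 21 days, of which 14/21 = 67% is at the higher dose. But this assumes that Cohort A is cut again cumulatively at that point, which no section says. If each cohort is cut at the end of its own PK phase, the contrast is clean.

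Finally, the analyses are descriptive, testing is not intended to support claims, and dose decisions go through the Safety Review Committee. This limits the consequence but does not make the table fit its stated purpose.

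**Conclusion.** The concern holds for the by-group AE table. Taken over the whole study, it cannot isolate a dose effect on either reading: cohort grouping shrinks an assumed doubling to about 1.004 at a constant rate (1.33 if half of AEs fall in week 1), and dose-at-onset grouping without person-time favours the lower dose artificially.

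The exposure figures rest on planned dosing. Actual person-days will differ: Section 3.8.2.2 reports four withdrawals, Section 9.1.1 one dose reduction, and Section 5.9 provides for replacement. Their dates, and the reduced dose, are not given, so any figure for the actual imbalance would be conjecture.

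A reader might infer that the trial's safety evaluation as a whole is compromised. It is not: all safety data are listed, and the overall AE summaries do not depend on the grouping. The point deserves a fix because the table has a stated purpose that it cannot serve, and the remedy is cheap.

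**What to change.** 1. In Section 7.2.2, limit the between-cohort AE comparison to the PK phase: Days 1-7 of each subject, counting Cohort A's AEs that start before its first 6,000 mg dose. Label it as 6 against 6, sequential, non-randomized and descriptive. The PK-phase interim can carry it if each cohort is cut at the end of its own PK phase.
2. For the whole study, tabulate AEs by actual daily dose at onset, with person-days and event rates beside subject counts. Include a place for any reduced dose: of those listed under Table 6, 4,500 and 2,000 mg BID (9,000 and 4,000 mg/day) match neither named group. State that dose is confounded with time on treatment, with dosing setting (inpatient away from meals in Section 4.5.1, at home near meals in Section 4.5.2) and with the selection of dose-reduced subjects for poor tolerability.
3. Delete the control subjects from Section 7.1.1; the study has no control group.

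The cost is SAP wording and modest programming. Sections 4.10 and 5.5.3 mention CRIS records, a diary and CRFs but do not say that dose-change dates are recorded, so their capture must be confirmed. The first-week contrast will remain coarse.
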